3.3. Number of Subjects

Considering the 2016 tumor registry-reported analytic case volume at each study site for thoracic, GI and Gyn cancers, 12 patients per month per site for each of surgical and medical oncology is a highly conservative estimate of accrual. With 6 sites, assuming equal cluster size, 432 patients will be enrolled both for each period and for each cohort. Thus, a minimum of 6048 patients are expected to be enrolled to the SW-CRT. (Table 3) We will not have a cap for the number of participants for each site. Thus, the number of participants at the end of the study will be different from site to site.

Table 3: Conservative estimates of the accrual numbers for the SW-CRT

Site	MO/ Surg	Period 1 (Run-in)	Period 2	Period 3	Period 4	Period 5	Period 6	Period 7	Total
BAPT	MO	72	72	72	72	72	72	72	504
	Surg	72	72	72	72	72	72	72	504
MMC	MO	72	72	72	72	72	72	72	504
	Surg	72	72	72	72	72	72	72	504
DFCI	MO	72	72	72	72	72	72	72	504
	Surg	72	72	72	72	72	72	72	504
LCI	MO	72	72	72	72	72	72	72	504
	Surg	72	72	72	72	72	72	72	504
DHMC	MO	72	72	72	72	72	72	72	504
	Surg	72	72	72	72	72	72	72	504
WVU	MO	72	72	72	72	72	72	72	504
	Surg	72	72	72	72	72	72	72	504
Total	MO	432	432	432	432	432	432	432	6048
	Surg	432	432	432	432	432	432	432	

Notes:

- The length of each period is 6 months. The run-in period will be at least 6 months, and it will be adjusted so that the total number of eligible episodes under the control condition can be identical to that under the intervention condition.
- The cells colored by blue or grey indicate the periods where the intervention is rolled out in that hospital.

A subset of eSyM+ patients will be asked to complete a research questionnaire called the “SASS Questionnaire (eSyM+ version)” asking about their Self-efficacy, Attainment of information needs, Symptom burden, and Satisfaction with care.

Table 4: SASS Questionnaire accrual numbers (Survey Cohort)							
Site	Surgery			Medical Oncology			Totals
	eSyM- Version	eSyM+ Version	eSyM+ Non-Responder Version	eSyM- Version	eSyM+ Version	eSyM+ Non-Responder Version	
Site 1	75	75	15	75	75	15	330
Site 2	75	75	15	75	75	15	330
Site 3	75	75	15	75	75	15	330
Site 4	75	75	15	75	75	15	330
Site 5	75	75	15	75	75	15	330
Site 6	75	75	15	75	75	15	330
Totals	450	450	90	450	450	90	1,980

eSyM+ : Intervention condition
eSyM- : Control condition

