4.7. Power Considerations

We estimate a minimum of 6048 patients will be enrolled. (see Section 3.3 for details). Since some subjects may experience more than one trigger event (see Section 4.2 General Analysis Approach: *Multiple episodes for medical record data*), the study participants will potentially contribute multiple data points. The goal of the power calculation for this study is to confirm that the study has sufficient power to assess the effects of the intervention on the outcomes. Therefore, for the power calculations throughout this SAP, we will conservatively estimate the power, assuming that an individual patient provides only one episode.

The probability that a patient who has a trigger event experiences EDTR within 30 days after the trigger event is estimated to vary between 8% to 15% for the control group, based on the HCUP data, institutional data, and early phase analyses from CMMI's Oncology Care Model for Baptist Memorial, the only Oncology Care Model participant among our 6 sites. We hypothesize that the probability of experiencing EDTR by Day 30 will be 3 to 4% lower in the eSyM+ group.

Table 9 shows the required sample sizes for the study to have 80% power to detect the difference between groups, at two-sided alpha level 0.05, using the SW-RCT design.¹⁴ Analyses of inter-institutional variation in hospitalization rates and ED visit rates from AHRQ's statewide databases indicate that low ICC estimates are appropriate.^{15,16} Furthermore, we expect a low ICC because: 1) the intervention will be deployed using the same technology across sites; 2) we will adjust for variation in baseline risk via GLMMs such that any potential differences in case-mix among sites will be negligible. Given these factors, the conservative estimate of 6048 participants provides adequate power to address the Aim 2a primary outcome.

Note that we used the sample size formula¹⁴ that assumes exchangeable correlations because we originally had planned to include sites as random effects. However, since the number of sites is only 6 in this study, we modified the analysis plan and decided to include sites as fixed effects in the primary analysis. We acknowledge that our original sample size calculation (above) may not be precise due to this, but it should still work as a conservative estimate.

Table 9. Required total sample size with various scenarios for 80% power					
The probability of experiencing EDTR by Day 30		Effect size		N required	

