5.1. Outcomes and summary measures

We do not have preliminary data to support a specific effect size. However, we expect that patients exposed to eSyM may be able to: 1) initiate adjuvant therapy sooner; and/or 2) remain on their chemotherapy regimens for longer duration. These time intervals are straightforward to measure from EHR encounter and date fields. The outcomes for Aim 2b and the projected minimum sample size are summarized in **Table 10**.

Table 10: Outcomes of Aim 2b					
Outcome	Type of outcome	Summary measure for each group	Summary measure for between-group difference	Cohort	Projected minimum sample size
Days from chemo regimen start date to stop date	Continuous	Mean*	Absolute Difference (AD)	All MO	504 patients/site; 3024 MO patients in total 1512 eSyM+ and 1512 eSyM-
Days from surgery date to start of adjuvant chemotherapy	Continuous	Mean*	AD	Surg who get adjuvant Rx (roughly 40% of all Surg)	202 patients/site; 1212 surg patients in total 606 eSyM+ and 606 eSyM-

* Because the maximum follow-up period of each episode is 1 year, the data will be truncated at 365 days when the mean value is calculated.

For MO patients, the outcome is time from the first dose to the last dose of a specific regimen. We will censor follow-up at 1 year. For Surg, the denominator population consists of patients who receive *any* adjuvant chemotherapy within 6 postoperative months. Tumor registry stage distribution at our 6 sites indicates that this will be 202 patients per site or 1212 in total.

The type of censoring involved in this analysis is only the truncation at the maximum follow-up period of 1 year. Thus, we will not employ censored time-to-event analysis methods but handle the outcomes as continuous outcomes.

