This change is necessitated by the observation that the majority of patients did not experience multiple episodes, leading to convergence issues with the generalized linear mixed-effects models initially planned as the primary analysis. Especially in Surgery cohort, only 2.8% subjects had multiple episodes under the intervention condition.

Changes to the Statistical Analysis Plan

1. Multiple episodes for medical record data (page 12)

Original:

- The primary analysis will include all these episodes other than the contaminated episodes.
- As sensitivity analyses, we will perform the analyses using the data consisting of only the first episode from each subject.

Revised:

- The primary analysis will include only the first episode from each subject.
- As sensitivity analyses, we will perform the analyses include all episodes other than the contaminated episodes.

2. Analysis Populations (page 15)

Original:

- 1) The primary analysis population consists of all eligible episodes under the intervention condition (A+B) (i.e., eSyM exposed) and all eligible episodes under the control condition (C) (i.e., eSyM unexposed).

- 2) The secondary analysis population consists of the episodes where patients engaged with eSyM (A) and the matched episodes during the pre-intervention period (C*).

Revised:

- 1) The primary analysis population consists of all 1st eligible episodes under the intervention condition (A+B) (i.e., eSyM exposed) and all 1st eligible episodes under the control condition (C) (i.e., eSyM unexposed).
- 2) The secondary analysis population consists of the 1st episodes where patients engaged with eSyM (A) and the matched 1st episodes during the pre-intervention period (C*).

3. Patient demographic and disease characteristics (Page 16)

Original:

- The unit of the analysis is not patient but episode. All eligible episodes eSyM- episodes will be included in this analysis.

Revised:

- The unit of the analysis is patient in the primary analysis. All eligible 1st episodes will be included in this analysis.

4. Multilevel Generalized Linear Regression Analysis (Page 16)

Original:

- The primary analysis for the outcomes in Aim 2 (Table 5) will be performed via multilevel generalized linear regression models (or generalized linear mixed-effects model; GLMM).
- Subjects
 - o We will potentially have more than one data point from one subject in this study.
 - o To take account of within-subject correlation, subjects will be included as random effects.

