 - o The primary analysis will consider random intercepts only.

Revised:

- The primary analysis for the outcomes in Aim 2 (Table 5) will be performed via generalized linear regression models (or generalized linear model; GLIM).
- Subjects
 - o We will potentially have more than one episode from one subject in this study. However, only the 1st episode from each patient will be included in the primary analysis.
 - o If possible, as a sensitivity analysis, we will perform multilevel generalized linear regression models (or generalized linear mixed-effects model; GLMM) by including all episodes. To take account of within-subject correlation, subjects will be included as random effects.

5. Sensitivity analyses (Page 19):

Original:

- Analysis with data from the first episode
 - o In the primary analysis, all episodes in the analyses except for eSyM- episodes contaminated with the eSyM intervention will be included. We will perform sensitivity analyses using only the first episode from each patient. In these sensitivity analyses, each patient will serve only one data point in the analysis.

Revised:

- Analysis with data from all episodes
 - o In the primary analysis, only the first episode from each patient will be used. In the primary analysis, each patient will serve only one data point in the analysis. We will perform sensitivity analyses using all episodes in the analyses except for eSyM- episodes contaminated with the eSyM intervention will be included.

Implementation and Documentation

These changes will be implemented immediately and documented in all relevant study documents and communications. The SAP addendum will be reviewed and approved by the IRB. All analyses will be conducted based on this SAP addendum.

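### The 6,048 in the Aim 2a power statement counts cohort entries, not unique patients; under the addendum's first-episode rule the planned minimum is between about 4,836 and 6,048 patients

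*SAP*

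**What the plan says.** SAP 3.3 starts from an accrual rate for each cohort: "12 patients per month per site for each of surgical and medical oncology is a highly conservative estimate of accrual". It then adds the cohorts: "432 patients will be enrolled both for each period and for each cohort. Thus, a minimum of 6048 patients are expected to be enrolled". Table 3 shows the same sum, 72 per site, period and cohort.

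SAP 4.7 assumes one episode per patient, calls that conservative, and applies it to the whole 6,048. It compares this with Table 9 and concludes that "the conservative estimate of 6048 participants provides adequate power to address the Aim 2a primary outcome".

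SAP 4.2 accepts that one patient can have several trigger events. It has exclusion rules for patients who cross between Surg and MO, and its worked example is a patient with a Surg episode followed by an MO episode. In SAP 5.1, Table 10 sizes the adjuvant population as "Surg who get adjuvant Rx (roughly 40% of all Surg", which is 202 per site and 1,212 in total.

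The addendum, change 1, now states: "The primary analysis will include only the first episode from each subject". Change 5 adds: "In the primary analysis, each patient will serve only one data point in the analysis". It revises five parts of the SAP; Sections 3.3 and 4.7 are not among them.

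**The concern.** Starting a new treatment plan for GI, gynecologic or thoracic cancer is the MO trigger (SAP 3.2 and 4.2). A surgical patient who goes on to adjuvant chemotherapy at the same site can therefore appear once in the 3,024 Surg accruals and again in the 3,024 MO accruals. A one-episode-per-patient analysis uses that person once. The power statement then refers to an N larger than the one the primary analysis would draw from the same accrual.

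The addendum also does not say whether the first episode means first overall or first within a cohort. This matters for the MO-only rows of Table 5, the separate MO and Surg analyses in SAP 4.2, and the MO-only panel of the Section 4.8 table shell. Read literally, patients whose surgery came first drop out of the MO-only sets. That changes who is analysed as well as how many.

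**Working it through.** **1. The plan's total.** 12 per month × 6 months = 72 per site, period and cohort. 72 × 6 sites = 432. 432 × 7 periods = 3,024 per cohort. 3,024 × 2 = 6,048, which reproduces the SAP exactly. No overlap term appears.

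**2. Unique patients.** If a fraction f of Surg patients is also among the MO accruals, N = 6,048 − f × 3,024. Table 10 gives 202 × 6 = 1,212 (40% of 3,024 is 1,210). Full overlap gives 6,048 − 1,212 = 4,836; no overlap gives 6,048.

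**3. Head-count against Table 9, low-ICC column.** The printed requirements are 2,192, 4,485, 5,047, 5,598, 3,246, 3,538, 3,823 and 4,103. 6,048 meets all eight; 4,836 misses 5,047 and 5,598. The 5,598 row fails once more than 6,048 − 5,598 = 450 patients overlap (15% of Surg). The 5,047 row fails above 1,001 (33%).

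**4. Reproducing Table 9.** The stepped-wedge (Hussey–Hughes) variance is

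Var = Iσ²(σ² + Tτ²) / [(IU − W)σ² + (U² + ITU − TW − IV)τ²],

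with I = 6, T = 7, U = 21 and W = V = 91, so the two brackets are 35 and 140. Here v is the mean of p(1 − p) over the two arms, n = N/42, σ² = (1 − ρ)v/n and τ² = ρv. Two-sided alpha is 0.05.

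- At ρ = 0.0001 the N for 80% power is 4,475, 5,037, 5,588, 3,236, 3,528, 3,813 and 4,093 for rows 2 to 8, each 10 below the printed value.
- The 8% v 5% cell does not reproduce (3,904 against 2,192).
- At ρ = 0.01, the column's label, no row reproduces (5,084 to 8,911).

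**5. Power at both ends of the range, ρ = 0.0001.** For 11% v 8%, v = (0.0979 + 0.0736)/2 = 0.08575.

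- N = 6,048: n = 144, SE = 0.01031, power = Φ(0.03/0.01031 − 1.96) = 82.9%.
- N = 4,836: n = 115.1, SE = 0.01148, power = Φ(0.03/0.01148 − 1.96) = 74.3%.

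| Control v eSyM | 6,048 | 4,836 | Loss (points) |
|---|---|---|---|
| 9% v 6% | 90.0% | 82.9% | 7.1 |
| 10% v 7% | 86.4% | 78.4% | 8.0 |
| 11% v 8% | 82.9% | 74.3% | 8.6 |
| 12% v 8% | 96.7% | 92.6% | 4.1 |
| 13% v 9% | 95.3% | 90.4% | 4.9 |
| 14% v 10% | 93.9% | 88.2% | 5.7 |
| 15% v 11% | 92.3% | 86.0% | 6.3 |

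The 8% v 5% row stays above 80% whether one uses the formula or the printed 2,192. Scaling from the printed N, Φ(2.80 × √(N/N_Table 9) − 1.96), gives 82.9% and 74.0% for 11% v 8%, a loss of 8.9 points. On that scaling, overlaps of 10%, 20%, 30% and 40% of Surg give 81.0%, 78.9%, 76.6% and 74.0%.

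**6. MO-only sets.** If all 1,212 are among the MO accruals and the first episode is taken overall, planned MO patients fall from 3,024 to 1,812, that is by 40%, all of them post-surgical.

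**The case against.** Several objections carry weight.

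- **The overlap is not stated.** The 1,212 comes from the tumor-registry stage distribution, and nothing says these patients are among the 12 per month counted for MO. Some patients operated on late in the trial would start chemotherapy after accrual closed. The addendum reports that only 2.8% of Surgery subjects had multiple episodes under intervention. If that counts later MO episodes, the overlap is small; the text does not say. This stands, and it is why the answer is a range.
- **The minimum is a floor.** SAP 3.3 sets no cap, SAP 3.6 adds Period 8, and the protocol (Section 5.0, Activity 5) reports more than 13,000 patients already collected. With eight periods the same sum is 6 × 8 × 72 × 2 = 6,912. Less 40% of 3,456 (1,382), that leaves 5,530, which meets the 5,047 row and is 68 short of 5,598. Every site is live in Period 8, so the head-count overstates its contribution to power. The 13,000 is not broken down by first episode, site, cohort and condition.
- **The addendum is not the sole cause.** SAP version 2.0 already excluded cross-cohort control episodes contaminated by earlier eSyM exposure, so not every surgery-then-chemotherapy episode was ever counted. SAP 4.7 already assumed one episode per patient. Both points stand.
- **Accrual is over.** Recalculated power changes no design decision, and the confidence interval will show the precision achieved. That limits the importance of the point, but the SAP would still contain a power claim tied to the wrong unit.

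A reader might infer that the trial is underpowered, or that 40% of MO patients are certainly lost. The documents support neither. Nor do they support a power loss for the Aim 2b MO outcome: the addendum states its rule for the Table 5 outcomes and does not mention Table 10.

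**Conclusion.** The point holds as a fault in the stated N and power. The 6,048 is a sum of cohort entries, while the primary analysis now uses unique patients. For the planned seven-period minimum that means about 4,836 to 6,048 patients. At the lower end two of Table 9's eight low-ICC scenarios fall below 80%, six do not, and the largest loss is about 9 points.

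The lower end assumes that every adjuvant patient is also a planned MO accrual. It counts only that source of overlap: chemotherapy before surgery, or repeat episodes within a cohort, could reduce the count a little further. The powers rest on ICC 0.0001. At the labelled 0.01 the 11% v 8% row would be 64% at 6,048 and 55% at 4,836, so the labelling of Table 9 is a separate matter that affects the baseline more than the overlap does.

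The missing within-cohort definition of the first episode is the more practical gap, because it decides which patients enter the MO-only results.

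**What to change.** 1. In SAP 3.3 and 4.7, relabel 6,048 as cohort entries. State the primary-analysis N as unique first-episode patients by site, cohort and condition, which can be counted without looking at outcomes. Restate the power at that N with the ICC actually used. The protocol repeats 6,048 in Section 5.0 (Activity 4), there as eSyM+ users, and in Section 6.0; the labels should agree.
2. Add to the addendum that analyses confined to one cohort (MO-only or Surg-only rows of Table 5, and the separate MO and Surg analyses) use each patient's first uncontaminated episode in that cohort. Say whether the same rule applies to Table 10.

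The cost is wording and one recalculation from the existing extract, with no new patients or data. Depending on the count, the stated power may become less favourable. The cohort-only sets would no longer be exact subsets of the combined primary set, and the SAP should say so.

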3.1. Randomization

This SW-RCT has 6 steps (figure below), and we randomize 6 sites (**Table 2**) to each of these steps. To ensure that two sites with the same region were not assigned to the same rollout step group (medical oncology live before surgery or surgery live before medical oncology), we employed a stratified randomization by region. As a result, each of the two groups has a site from each of the three regions (Northern, Southern, and Metropolitan). The stepped wedge design includes seven time-periods, including a run-in period (Figure).

Figure: SIMPRO Stepped-Wedge Randomization Schema

Abbreviations: BAPT=Baptist, WVU=West Virginia University, MMC=Maine Medical Center, DHMC=Dartmouth Hitchcock Medical Center, LCI=Lifespan Cancer Institute, DFCI=Dana-Farber Cancer Institute, SIMPRO=Symptom Management Implementation of Patient Reported Outcomes in Oncology

Sequence	Group	Site	eSyM version	Period 1	Period 2	Period 3	Period 4	Period 5	Period 6	Period 7
				Mar '19 - Aug '19	Sep '19 - Feb '20	Mar '20 - Aug '20	Sep '20 - Feb '21	Mar '21 - Aug '21	Sep '21 - Feb '22	Mar '22 - Aug '22
Med Onc live Before Surgery	Southern	BAPT	Med	Pre-live	Live					
			Surg	Pre-live						Live
	Northern	MMC	Med	Pre-live		Live				
			Surg	Pre-live					Live	
	Metrop-olitan	DFCI	Med	Pre-live			Live			
			Surg	Pre-live				Live		
Surgery live Before Med Onc	Metrop-olitan	LCI	Med	Pre-live				Live		
			Surg	Pre-live			Live			
	Northern	DHMC	Med	Pre-live				Live		
			Surg	Pre-live		Live				
	Southern	WVU	Med	Pre-live					Live	
			Surg	Pre-live	Live					

Note: The timing of medical and surgical rollouts is not the same at each site in this SW-RCT. The timing of medical and surgical rollouts was determined so that the number of subjects on the intervention and control would be the same in each site, when medical and surgical cohorts were combined.

Table 2: Six participating sites and Region

Site	Region
WVU	Southern
BAPT	
DHMC	Northern
MMC	
DFCI	Metropolitan
LCI	

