4.2. General Analytic Approach

[figure not shown]
Medical Oncology and Surgery:

- The primary analysis will include data from both medical oncology (MO) and surgery (Surg) and estimate a common effect of the intervention in MO and SO. An indicator variable (MO vs. Surg), interaction between MO/Surg and Site, and interaction between MO/Surg and background time trend will be included as covariates for adjustment in multilevel generalized linear regression models.
- As a secondary analysis, for each outcome, the heterogeneity of the intervention effect by MO/Surg will also be assessed by the test for interaction between the intervention (eSym yes/no) and MO/surg using multilevel generalized linear regression models. In this analysis, the interaction between the intervention and MO/Surg will be added to the model for the primary analysis.
- As another secondary analysis, we will analyze the data from MO and Surg separately and estimate the intervention effect for each outcome. Note that this analysis is similar to the aforementioned secondary analysis including the interaction between the intervention and MO/Surg. While the aforementioned secondary analysis assumes common effects of patients' characteristics (such as age, race, gender and so on) across MO and Surg, this analysis consider these are possibly different between MO and Surg.

Determination of the intervention and length of follow-up for each episode:

- The presence /absence of the intervention (eSym+ vs. eSym-) is determined in a cross-sectional way at the time of the occurrence of the trigger event
- The follow-up period for each episode is one year from the chemotherapy start date (**MO**) and the date of discharge (**Surg**)

- The intervention determined at the trigger event will never change during the one-year of follow-up period unless another trigger event occurs (see Figure below)

- Some subjects may experience more than one trigger event (i.e., a new chemotherapy treatment plan for **MO** and a qualifying procedure for **Surg**) during the study. Thus, potentially, multiple data points/episodes will be collected from one patient.
- The primary analysis will include all these episodes other than the following episodes:
 - MO episode where its trigger event occurred after the patient was exposed to eSyM Surg, but before eSyM MO was rolled out in the patient's site.

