4.4. Multilevel Generalized Linear Regression Analysis

The primary analysis for the outcomes in Aim 2 (Table 5) will be performed via multilevel generalized linear regression models (or generalized linear mixed-effects model; GLMM).⁹ The null hypothesis for the statistical test is no intervention effect on the outcome, which indicates that the regression coefficient for the intervention indicator variable is zero. The intervention effect will be summarized in both absolute and relative terms (CONSORT Checklist Item 17b).⁷

Followings are specifications of the GLMM for the primary and secondary analyses.

- Link function
 - For binary outcomes, the logit-link will be used.
 - For count outcomes, the log-link will be used, and the follow-up time will be included as the offset in the model. (Poisson regression)
 - For time-to-event outcomes, we will use Poisson regression models, where the log-link will be used. The event indicator (1: event, 0: censoring) will be the response variable. Exposure time (i.e., days from the start date of the follow-up to either the date of the event occurrence or the end of follow-up, whichever comes first) will be included as the offset in the model.
- Treatment effect metrics
 - Following the recommendation of the CONSORT guideline,⁷ we will report the treatment effect in both absolute and relative metrics.
 - For binary outcomes, we will report odds ratio (OR) derived from the GLMM with the logit-link. In addition, we will calculate absolute difference (AD), using the resulting GLMM with G-computation. Bootstrap will be used to obtain a standard error for the estimated AD.
 - For count outcomes and time-to-event outcomes, we will report the incidence rate ratio (IRR) derived from the GLMM model. In addition, we will calculate absolute difference in incidence rate (i.e., incidence rate difference;IRD) in a similar way to calculate AD.
- Secular trend
 - Primary: Calendar time of the start date of the follow-up of each episode will be included as a continuous variable with natural cubic spline with 3 knots
 - Secondary: Period in which the trigger event occurs will be included as a categorical variable.
- Site (cluster)

- Since there are only 6 sites in this study, the conventional analysis of including cluster as random-effects is problematic due to this small number.¹⁰
- Primary: The primary analysis includes sites as fixed effects.

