- Secondary: Sites will be included as random-effects with a small sample adjustment (the Kenward-Roger method).^{11,12}
- Subjects
 - We will potentially have more than one data point from one subject in this study.
 - To take account of within-subject correlation, subjects will be included as random effects.
 - The primary analysis will consider random intercepts only.
- Variables to be included the GLMM
 - **Table 8** lists the variables selected based on the study design (Category A) and clinical importance (Category B and C).
 - The primary analysis includes the variables in Category A and B.
 - As a secondary analysis, we will perform the same analysis including Category A, B and C.

Table 8: Variables that will or may be included in the generalized linear mixed-effects model for the primary analysis

Variable	Category A	Category B	Category C
Intervention indicator: (eSyM+ vs. eSyM-)	X		
Cohort (MO vs. Surgery)	X		
Calendar Time (Secular trends) [continuous with natural cubic spline]	X		
Site (Treating Facility) (DFCI, MMC, DHMC, LCI, BAPT, WVU) [as fixed effects]	X		
Interaction between Cohort (MO vs. Surgery) and Calendar Time (Secular trends)	X		
Interaction between Cohort (MO vs. Surgery) Site (Treating Facility) (DFCI, MMC, DHMC, LCI, BAPT, WVU) [as fixed effects]	X		
Subjects [as random effects (random intercepts only)]	X		
Goal of Chemotherapy (MO with curative goal, MO with palliative goal, Others)		X	
Age (years) (fractional polynomials)		X	
Sex (male vs. female)		X	
Race/Ethnicity (white/non-Hispanic, black/non-Hispanic, Hispanic, Other/Unknown)		X	
Rurality based on zip code (large metro, small metro, suburban, rural)		X	
Cancer/procedure type (GI, Gyn, Thoracic)		X	
Employment (Employed, Disabled, Retired, Other)			X
Marital status (Married vs. Not married)			X
Insurance type (Medicare only, Medicare and Medicaid, Medicaid only, Private, Other)			X
Socio-economic status (quintiles by the zip code-based poverty level)			X
Co-morbidity (Charlson comorbidity index from encounter diagnoses in the 12 months before the first eligibility date) (0, 1, 2+)			X

- Time decay of the intervention effect

- As a sensitivity analysis, we will include the interaction between the intervention and time from the rollout of the intervention condition at the treating site to the time of the trigger event, where we treat the time as a categorical variable in the model.

Considerations on the potential informative censoring

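### SAP 4.7 calls Table 9 conservative and 6048 patients adequate, but no power calculation covers the primary model's site-by-cohort terms; with them, 6048 in total gives 80% power in about 2 of 8 scenarios

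*SAP*

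**What the plan says.** SAP 4.7 states: "Given these factors, the conservative estimate of 6048 participants provides adequate power to address the Aim 2a primary outcome". It discloses that Table 9 came from a formula with exchangeable correlation and random sites, that the primary analysis now fits sites as fixed effects, and that the calculation "may not be precise due to this, but it should still work as a conservative estimate". It claims a further margin: "we will conservatively estimate the power, assuming that an individual patient provides only one episode".

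The primary model contains more than site main effects. SAP 4.2 says that "interaction between MO/Surg and Site, and interaction between MO/Surg and background time trend will be included as covariates for adjustment", and Table 8 puts both interactions in Category A, which the primary analysis uses. Under SAP 4.4, calendar time "will be included as a continuous variable with natural cubic spline with 3 knots".

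SAP 3.1 explains that rollout was timed so that the "number of subjects on the intervention and control would be the same in each site, when medical and surgical cohorts were combined".

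The Addendum of June 2024 changes the analysis set: "The primary analysis will include only the first episode from each subject". It keeps both interactions and does not revise 4.7.

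**The concern.** The design balances intervention and control within a site only when the two cohorts are pooled. A separate intercept for each site-cohort gives up that balance. Each of the 12 site-cohorts then acts as its own cluster, and most are far from 50/50. This costs information, and Table 9 does not count the cost.

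The one-episode margin has also gone. Once the primary analysis uses only first episodes, one episode per patient is exact and no longer conservative.

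If the trial is null, readers will judge it against 4.7, which tells them that power was adequate and that any error is on the safe side.

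**Working it through.** **Inputs.** Two-sided alpha 0.05, 80% power and the eight risk pairs (SAP 4.7, Table 9). Six sites, two cohorts, seven periods and 72 patients per site-cohort-period, so 84 × 72 = 6048 (SAP 3.3). Medical oncology (MO) goes live in periods 2 to 7 across the sites and Surgery in the mirror order 7 to 2, which gives the within-site balance described in SAP 3.1.

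**Step 1: reproduce Table 9.** The SAP cites its formula but does not print it. I used the standard stepped-wedge design effect with 6 steps, one baseline period, ICC ρ and cell size m = N/42:

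N = N_ind × 7 × {[1 + ρ(7m − 1)] / [1 + ρ(4m − 1)]} × 3(1 − ρ) / [2(6 − 1/6)]

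N_ind is the two-proportion total, with variance pooled under the null and unpooled under the alternative. For 9% vs 6%, N_ind = 2417.7. With ρ = 0.0001 and m = 106.8, N = 2417.7 × 1.8 × (1.07465/1.04261) × 0.9999 = 4485, the printed figure.

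- ρ = 0.0001: 3914, 4485, 5047, 5598, 3246, 3538, 3823, 4103.
- ρ = 0.005: 5893, 6816, 7721, 8606, 4810, 5283, 5746, 6198.
- ρ = 0.01: 6198, 7128, 8039, 8928, 5101, 5581, 6049, 6505.
- ρ = 0.05: 6253, 7151, 8028, 8883, 5194, 5658, 6110, 6550.

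Fourteen of 16 printed cells match to the patient at 0.0001 and 0.005; the column heads say 0.01 and 0.05. The exceptions are 2192 (computes as 3914) and 5844 (computes as 5893). At a true ICC of 0.01, 2 of 8 rows fit within 6048 and a third needs 6049; at 0.05, 2 of 8 fit.

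**Step 2: design effect of the primary model.** Design effect = (84 × 0.25) / RSS = 21 / RSS, where RSS is the residual sum of squares of the live/not-live indicator after the other model terms. With categorical periods, for one cohort:

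- 21 of 42 cells are live, so the indicator's sum of squares is 21 and its grand-mean term is 21²/42 = 10.5.
- Period totals 0 to 6 give 91/6 = 15.17. Site totals 1 to 6 give 91/7 = 13.
- Site main effects only: every site has 7 of 14 cells live, so they remove nothing beyond cohort-by-period. RSS = 2 × (21 − 15.17) = 11.67 and the design effect is 1.80.
- Site-by-cohort: RSS = 2 × (21 − 15.17 − 13 + 10.5) = 6.67 and the design effect is 3.15.

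With the planned spline by cohort, and entry spread evenly within periods, these become 1.77 and 3.07. The latter is 3.065 to 3.068 over four knot placements.

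**Step 3: required N and power.** Required N = unpooled two-proportion N × design effect (within-site-cohort correlation taken as zero). First row: 2112.2 × 3.068 = 6480. Power is from the logistic information matrix at 6048.

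| Control vs eSyM+ | Table 9 low | Table 9 moderate | N, site main effects | N, primary model | Power at 6048 |
|---|---|---|---|---|---|
| 8% vs 5% | 2192 | 5844 | 3745 | 6480 | 77% |
| 9% vs 6% | 4485 | 6816 | 4277 | 7400 | 72% |
| 10% vs 7% | 5047 | 7721 | 4796 | 8299 | 67% |
| 11% vs 8% | 5598 | 8606 | 5303 | 9176 | 62% |
| 12% vs 8% | 3246 | 4810 | 3117 | 5393 | 84% |
| 13% vs 9% | 3538 | 5283 | 3392 | 5869 | 81% |
| 14% vs 10% | 3823 | 5746 | 3660 | 6332 | 78% |
| 15% vs 11% | 4103 | 6198 | 3921 | 6784 | 75% |

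With site main effects only, all eight rows fit and 15 of 16 Table 9 cells are larger than needed. With the primary model, the requirement is 7–12% above the moderate column and 64–66% above the low column (2192 excluded). The detectable difference at 6048 is 3.1, 3.5, 4.0 and 4.2 points at control risks of 8, 10, 13 and 15%.

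**Step 4: variants.**

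- At 6048: categorical periods 61–83%, 2 of 8 (1 of 8 with the go-live periods in SAP 3.6); actual go-live dates with spline 63–85%, 2 of 8; spline with requirements multiplied by (1 − 0.05) for ICC 0.05, 3 of 8.
- With Period 8 at the minimum rate (96 × 72 = 6912): 66–88%, 4 of 8 (2 to 3 with categorical periods).
- With the Protocol's January 2018 to March 2024 window at 12 per month (75 × 12 × 12 = 10,800): 76–96%, 6 to 8 of 8.
- With 6048 eSyM+ users and equal controls (12,096): 80–99%, all 8.
- With the 13,000 patients in Protocol Activity 5, if all are analysable (assumption): 83–99%, all 8.

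**The case against.** The sentence about conservatism concerns only the change from random to fixed sites, and on that change it is right. In the adequacy sentence, conservative describes the accrual estimate. Both points stand, but the adequacy conclusion is about the primary outcome and so has to hold for the primary model, which it does not.

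Much of the gap to Table 9 comes from the ICC labels. At a true ICC of 0.05 the cited formula (6253 in the first row) exceeds the primary model's requirement (6480 × 0.95 = 6156) in all eight rows. At 0.01 it is about 3% short in that row (6198 vs 6480 × 0.99 = 6415). This is a fair correction on cause. It does not rescue 4.7, because the correctly labelled formula also fits only 2 of 8 rows within 6048. The count at 0.01 becomes 3 of 8 if variance is fully unpooled.

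Counting rows at an 80% threshold is coarse: two failing rows sit at 77–78%, and only the 9–11% control-risk rows fall clearly short.

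Finally, 6048 is a floor. Accrual is uncapped, Period 8 was added, and the Protocol's Section 6 table supports reading 6048 as the trial total, so its reference to 6,048 eSyM+ users may be loose wording. All true, but 4.7 rests its claim on 6048, and the two readings give 2 of 8 and 8 of 8.

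**Conclusion.** The power statement in SAP 4.7 is wrong as written. For the specified primary model and 6048 patients in total, power is 62–84% and reaches 80% in about 2 of 8 of the SAP's own scenarios; every Table 9 entry is below the number needed. Table 9 also carries ICC labels that do not match its figures, and two wrong cells. The ICC diagnosis is inferred from the cited formula. SAP Table 11 prints its lowest ICC as 0.01%, so the low label may have lost a percent sign; that would not explain the moderate label.

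This rests on equal cells of 72, the mirrored schedule, an assumed knot placement and no Category B covariates in the calculation. It does not show that the completed trial is underpowered: at 12,000 to 13,000 analysable patients all eight scenarios pass.

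**What to change.** - Remove the sentence calling the calculation conservative, and the claim of a margin from one episode per patient.
- Relabel Table 9 with the ICCs actually used, or recompute it at the intended ones, and correct the 2192 and 5844 cells.
- Add a column for the actual primary model: site-by-cohort fixed effects, cohort-specific spline, first episodes only. State which scenarios 6048 covers.
- Give power and the minimum detectable difference at 6048 and at the achieved number, including Period 8.
- Reconcile the Protocol's 6,048 eSyM+ users (Activity 4, number of subjects) with the SAP's 6048 in total (3.3 and 4.7). State which accrual window applies: SAP 3.6 or the Protocol's denominator definition.

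The cost is SAP wording and one recalculated table, with no change to design or data. Stated power at the minimum number becomes less favourable.
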